12.4 Replacement of Subjects

Subjects who withdraw from the study treatment will be replaced.

12 PROTOCOL VIOLATIONS

A protocol violation occurs when the subject, investigator, or Sponsor fails to adhere to significant protocol requirements affecting the inclusion, exclusion, subject safety and primary endpoint criteria. Protocol violations for this study include, but are not limited to, the following:

- Failure to meet inclusion/exclusion criteria
- Use of a prohibited concomitant medication
- Non-compliance with study drug regimen

Failure to comply with Good Clinical Practice (GCP) guidelines will also result in a protocol violation. The Sponsor will determine if a protocol violation will result in withdrawal of a subject.

When a protocol violation occurs, it will be discussed with the investigator and a Protocol Violation Form detailing the violation will be generated. This form will be signed by a Sponsor representative and the Investigator. A copy of the form will be filed in the site's regulatory binder and in the Sponsor's files.

Compliance will be monitored closely. Non-compliant patients who use the treatment fewer than 2 times a day for more than 2 weeks (as determined by review of the treatment diary at the week 4 visit) will be considered unevaluable for the primary endpoint and replaced with new patients. These patients, however, will be included in the toxicity report. During the four-week period when patients are receiving study treatment, additions of new immunomodulatory medications (systemic or topical in the mouth) are allowed, but these patients will be regarded as unevaluable for the primary endpoint and will be replaced.

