15 ADMINISTRATIVE, ETHICAL, REGULATORY CONSIDERATIONS	29
15.1 Protocol Amendments	30
15.2 Institutional Review Boards and Independent Ethics Committees	30
15.3 Informed Consent Form	30
15.4 Publications	31
15.5 Investigator Responsibilities	31
16 APPENDICES	35
Appendix 1: Patient instructions	35
Appendix 2: Treatment diary	35
Appendix 3: Visit #1 CRF	35
Appendix 4: Visit #2 CRF	35

LIST OF ABBREVIATIONS

AE	adverse event
CFR	Code of Federal Regulations
CRF	case report form
DMC	Data Monitoring Committee
DSMB	Data Safety Monitoring Board
FDA	Food and Drug Administration
GCP	Good Clinical Practice
cGVHD	chronic graft versus host disease
HIPAA	Health Insurance Portability and Accountability Act of 1996
ICF	informed consent form
ICH	International Conference on Harmonisation
IEC	Independent Ethics Committee
IRB	Institutional Review Board
OLP	Oral lichen planus
PI	Principal Investigator
SAE	serious adverse experience

PROTOCOL SYNOPSIS

TITLE	DEXAMETHASONE SOLUTION AND DEXAMETHASONE IN MUCOLOX™ FOR THE TREATMENT OF ORAL INFLAMMATORY ULCERATIVE DISEASES
SPONSOR	Professional Compounding Centers of America
FUNDING ORGANIZATION	
NUMBER OF SITES	1
RATIONALE	Topical steroid therapy is considered the first line of treatment for Oral Inflammatory Ulcerative Diseases with current treatment regimens requiring multiple application or rinses daily. Although topical steroid therapy can be successful for most patients, the treatment schedule can be challenging to maintain. There is therefore considerable interest in developing new and more effective therapies that require less frequent applications. The possibility of having a treatment agent that is safe, easy to use, and cost effective, with potentially greater efficacy than the current standard of care available topical steroid solutions would be ideal. Using Mucolox™ as a vehicle to deliver topical dexamethasone to the oral mucosa has the potential to effectively prolong contact time between the medication and mucosa, leading to improved clinical outcomes due to the need for less frequent application. This technology would help to more efficiently achieve high drug concentrations locally. By possibly shortening the frequency and time of topical therapy and improving patient compliance, this may translate to greater therapeutic benefit.
STUDY DESIGN	This is a randomized, phase 2 study.

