4 STUDY DESIGN

4.1 Study Overview

This is a single center, 4-week, open label randomized, phase II study. Randomization will be conducted by the UCSF Investigational Drugs Services (IDS) Pharmacy. The study period will be four weeks, which based on previous studies should be an adequate period to assess significant clinical improvement. Subjects will be evaluated clinically at baseline before starting treatment and at the end of the four-week period, for a total of two visits. Subjects will be randomized to either compounded dexamethasone in Mucolox™ or commercial dexamethasone solution only. Subjects will return for evaluation after four weeks at which time the primary end-points will be assessed. Screening data will be reviewed to determine subject eligibility. Subjects who meet all inclusion criteria and none of the exclusion criteria will be entered into the study.

The following treatment regimens will be used:

Experimental treatment: Dexamethasone solution (0.5mg/5ml) in Mucolox™

Comparator: Commercial Dexamethasone solution (0.5mg/5ml)

Total duration of subject participation will be four weeks. Total duration of the study is expected to be 4-5 weeks.

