8.2 Blinding

This is an open label trial with no blinding.

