8.3 Formulation of Test and Control Products

8.3.1 Mucolox™

Description

Mucolox™ (PCCA, Houston, TX 77099) is a mucoadhesive polymer designed to improve mucoadhesion and prolong retention of medications at application sites within the oral mucosa. The composition of Mucolox™ is outlined in the table below.

Ingredient Name	INCI Name/Technical Name	Classification	FDA Reference
Potassium Sorbate NF	Potassium Sorbate	Subpart D – Chemical Preservatives	21 CFR 582.3640
Sodium Benzoate NF	Sodium Benzoate	Subpart D – Chemical Preservatives	21 CFR 582.3733
Glycerin USP (Natural)	Glycerin	Subpart B – General Purpose Food Additive	21 CFR 582.1320
Edetate Disodium USP Dihydrate	Disodium EDTA	FDA has no questions regarding intended use.	GRN000363
Pullulan	Pullulan	FDA has no questions regarding intended use in certain foods.	GRN000099
Tamarindus Indica Seed Polysaccharide	Tamarindus Indica Seed Polysaccharide	FDA has no questions regarding intended use.	GRN000503
Isomalt	Isomalt	Self-Determined GRAS (1996)	GRN6G0321
Simethicone USP	Simethicone	Used in Various Routes, Dosage Forms and Maximum Potencies	UNII: Multiple (Mixture)
Sodium Hyaluronate	Sodium Hyaluronate	Used in Various Routes, Dosage Forms and Maximum Potencies	UNII: YSE9PPT4TH
Poloxamer 407	Poloxamer 407	Used in Various Routes, Dosage Forms and Maximum Potencies	UNII: TUF2IVW3M2
Zea Mays (Corn) Starch	Zea Mays (Corn) Starch	Used in Various Routes, Dosage Forms and Maximum Potencies	UNII: O8232NY3SJ
Carbomer	Carbomer	Used in Various Routes, Dosage Forms and Maximum Potencies (Type: Proprietary)	UNII: Type Proprietary
Water	Water	N/A	UNII: 059QF0K00R

Compatibility

N/A

Handling

There are no special handling requirements.

Availability

Compounded dexamethasone solution in Mucolox™ will be dosed at a concentration of 0.5 mg/5mL and dispensed through the UCSF Investigational Drugs Services Pharmacy. The prescription for the patients in ARM B (dexamethasone) will also be dispensed through the UCSF Investigational Drugs Services Pharmacy.

Preparation

Study subjects will be given a kit with the following, including detailed written instructions (see Appendix 1):

ARM A

- A four week supply of compounded dexamethasone solution in Mucolox™ will be dispensed, with extra for error and spillage, which will be rounded to 480 mL bottle at a concentration of 0.5 mg/5mL.
- Small dosing cups

Administration

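### In an open-label trial, the sponsor may decide, with no criteria, cut-off or masking, which protocol violators are withdrawn, and nothing keeps their scores in the primary comparison

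*Combined protocol and SAP*

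**What the plan says.** - **Who decides.** Section 12 (Protocol Violations): "The Sponsor will determine if a protocol violation will result in withdrawal of a subject". No criterion, deadline, masking or independent review is attached.
- **What counts.** The same section opens its list with "Protocol violations for this study include, but are not limited to, the following", so the list is open-ended.
- **Who the sponsor is.** The synopsis names "Professional Compounding Centers of America". Section 8.3.1 attributes Mucolox to a firm with the initials PCCA. That the two are the same company is inferred from the matching initials.
- **Blinding.** Section 8.2: "This is an open label trial with no blinding".
- **Timing.** There are two visits. Section 4.1 says of the second: "Subjects will return for evaluation after four weeks at which time the primary end-points will be assessed". Section 12 judges its compliance threshold "as determined by review of the treatment diary at the week 4 visit", which is the same visit.
- **Fixed rules.** Section 12 makes two groups unevaluable for the primary endpoint and replaces them: those rinsing fewer than 2 times a day for more than 2 weeks, and those given a new immunomodulatory drug. Section 9.2 also makes the second group unevaluable.
- **Safeguards.** Section 12 requires that a violation be discussed with the investigator and that a form be signed by both parties and filed. Section 12.3 requires a recorded reason for withdrawal.
- **Replacement.** Section 12.4: "Subjects who withdraw from the study treatment will be replaced".
- **Data access.** Section 14.5 gives the sponsor's representatives access to study data on request.

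**The concern.** The party with a commercial interest in Arm A holds an uncriteria'd choice over which violators leave a comparison of 15 per arm. Everyone knows the arm, and the endpoint is a patient-reported score. If the choice were made with the week-4 score in view, even in good faith, it could tilt the difference towards Arm A, because a poor Arm A score could be exchanged for a fresh draw. A reader of a positive result would have no means in the protocol to rule this out. The defect is in the rule. No misconduct is alleged.

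**Working it through.** The plan gives no figure on this point, so the check has two parts: what the text leaves open, and how much that could matter.

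**1. What is left to discretion**

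| Violation | Consequence in Section 12 | Sponsor's choice? |
|---|---|---|
| Fewer than 2 rinses a day for more than 2 weeks | Unevaluable, replaced | None on evaluability |
| New immunomodulatory drug | Unevaluable, replaced | None on evaluability |
| Lesser non-compliance | None stated | Yes |
| Eligibility failure | None stated | Yes |
| GCP breach, or anything unlisted | None stated | Yes |
| Prohibited concomitant medication | None stated | Yes, and the category is unclear |

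The last row is unclear because the synopsis lists no prohibited medication and Section 7 sets no restrictions, while Section 9.2 bars other agents given to treat the disease. These passages must be reconciled.

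**2. Does anything keep the score in the analysis?** Sections 13.1.1 and 13.1.2 name tests but no analysis population. Section 13 promises a SAP before the final data are analysed. In an open-label trial that can be after individual results are known. So the text neither drops nor retains a withdrawn subject's score.

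**3. Illustrative size**

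Inputs from Section 13.2: 15 per arm, SD of change 1.4, two-sided alpha 0.05. Section 13.1.1 gives the t-test as one of its two options. Assumptions not in the documents: no true difference, normal scores, violations unrelated to outcome, *v* violators per arm, and the *k* least favourable to Arm A replaced by new random patients.

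Expected shift per arm = 1.4 × (sum of the *k* most extreme expected normal order statistics out of *v*) / 15.

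- 1 of 3: 1.4 × 0.846 / 15 = 0.079 per arm, or 0.158 with both arms.
- 2 of 5: 1.4 × (1.163 + 0.495) / 15 = 0.155 per arm, or 0.309 with both arms.
- 2 of 15: 1.4 × (1.736 + 1.248) / 15 = 0.278 per arm, or 0.557 with both arms.

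Simulation of 200,000 null trials per row:

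| Replaced | Spurious difference (points) | Two-sided error | False wins for Arm A |
|---|---|---|---|
| None | 0.00 | 5.0% | 2.5% |
| Worst 1 of 3, Arm A only | 0.08 | 5.3% | 3.6% |
| 1 of 3 in each arm | 0.16 | 5.9% | 4.9% |
| Worst 2 of 5, Arm A only | 0.15 | 5.9% | 4.7% |
| 2 of 5 in each arm | 0.31 | 9.1% | 8.6% |
| 2 of all 15 in each arm (ceiling) | 0.56 | 25.2% | 24.9% |

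The simulated shifts agree with the formula. A repeat with another seed changed the error rates by at most about 0.3 percentage points. The last row requires the most extreme patients in each arm all to have a recordable violation, so it is an upper limit and not a scenario to plan for.

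**The case against.** **Timing.** A reader might infer that the sponsor decides after seeing the week-4 score. No passage says so. Section 12.3 describes withdrawal as happening before Visit 2, and access on request under Section 14.5 makes prior sight possible without establishing it. This stands: the timing is not excluded, and no more can be said.

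**Loss from the analysis.** A reader might also infer that a withdrawn subject's score is dropped. The text does not say that either. Section 12.4 replaces those who withdraw from study treatment, which does not plainly cover someone who finished 28 days, and Section 11.1 encourages subjects who stop treatment to complete their visits. This stands too. The gap is that nothing retains the score.

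**Section 12.3 as a second open power.** It is not one. It lets the sponsor withdraw a subject at any time, but only where continuing is felt not to be in the subject's best interest. The point rests on the Section 12 sentence alone.

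**Existing safeguards.** The two fixed rules remove much of the discretion over compliance, and many eligibility failures can be known at entry. Investigator discussion and a co-signed, filed form would leave a trail of selective withdrawals. These reduce the risk. They do not mask the decision, and no investigator veto is stated.

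**Size.** The large error rates need free choice among all 15 patients. With a few violators the inflation is modest.

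**Conclusion.** The point holds as a gap in governance and in the analysis set. Section 12 gives an apparently interested sponsor an unmasked decision without criteria, and Section 13 does nothing to make that decision harmless to the primary comparison. Under the stated assumptions, selective use on 1 of 3 violators per arm would raise false wins for Arm A from 2.5% to about 4.9% (two-sided error about 6%). With 2 of 5 per arm they would rise to about 8.6% (about 9%). These are sensitivity figures. The documents give no violation rate, and if violators were withdrawn without regard to outcome there would be no inflation of this kind. It would go too far to conclude that a positive result could not be believed: the documents show that selection is possible, not that it is planned or likely. The change should be made because it is cheap and settles the question whatever the timing turns out to be.

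**What to change.** 1. In Section 12, replace the sponsor-decision sentence with: *Protocol violations are recorded and classified as major or minor by criteria written before any Visit 2 score is reviewed. A violation does not by itself end follow-up, and all randomised subjects with a Visit 2 score are included in the primary analysis in the arm assigned.*
2. In Section 13, name that group as the primary analysis set.
3. Move the two unevaluability rules in Section 12, and the matching one in Section 9.2, to a per-protocol sensitivity analysis. If they stay where they are, they contradict item 1.
4. State that a replaced subject's available data are kept.
5. Leave Section 12.3 (best-interest withdrawal) and Section 11.1 unchanged. Nothing here alters a clinical rule.

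**Cost.** A short amendment to three sections, plus written classification criteria before the first Visit 2 score is reviewed. The sponsor loses a discretion. The primary estimate will include violators and so may be slightly diluted; the per-protocol analysis shows by how much. Subjects with no Visit 2 score are not covered by this change, and the SAP still has to say how they are handled.

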7 CONCURRENT MEDICATIONS

There will be no restrictions on concomitant medications or supportive care measures.

All subjects will be treated with fluconazole 200 mg tablets once-a-week dosing for prophylaxis as topical steroid therapy may increase the risk of candidiasis. This is typically very effective at preventing candidiasis in susceptible patients, and since there are no interim clinical visits, this will minimize the risk of secondary infection, which if not detected early, could confound the results at the week 4 evaluation. A single weekly dose of fluconazole is not sufficient to have an impact on therapeutic levels of other medications. Fluconazole is a pregnancy category D drug. As such, pregnant women will be excluded from this study.

Any subjects that are already taking a systemic antifungal medication at the time of study enrollment will continue their prescribed medication and will not need to take the additional weekly fluconazole dose.

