9.2 Study procedures

Potentially eligible subjects will be screened by one of the investigators by asking patients to rate their worst oral pain or pain score (0-10) over the previous week on a VAS. Those answering with at least a score of “7” (1/10) and that meet all other eligibility requirements (see Section 6) will be eligible for enrollment. All patients will sign informed consent for study participation. Each study visit is anticipated to take approximately 45 minutes. A urine pregnancy test will be performed for women of child bearing potential.

There is no financial compensation for participating in this study. Treatment will be administered on an outpatient basis. Study medication will be prescribed by authorized study staff physicians and filled by the Investigational Pharmacy at no expense for the patient. No investigational or commercial agents or therapies other than those described below may be administered with the intent to treat the participant’s Oral Inflammatory Ulcerative Diseases.

Subjects will be evaluated clinically at baseline before starting treatment and at the end of the four-week period, for a total of two visits. Comprehensive subjective and objective data will be collected (Appendix 3 & 4) and intraoral photographs will be obtained. Oral mucosal disease will be evaluated using both patient reported (questions/visual analog scales) and clinician assessed measures.

Subjects will be prescribed compounded dexamethasone 0.5mg/5ml solution in Mucolox™ (ARM A) or commercial dexamethasone 0.5mg/5ml solution only (ARM B). All subjects will also receive a prescription for fluconazole 200 mg tablets once-a-week as prophylactic antifungal therapy. Any subjects that are already taking an antifungal oral medication at the time of the study enrollment will continue their prescribed medication and will not need to take the additional weekly fluconazole dose. Subjects will return for evaluation after four weeks at which time the study endpoints will be assessed.

If there is worsening of Oral Inflammatory Ulcerative Diseases that requires initiation of new immunomodulatory medications (systemic or topical), patients will remain on treatment, but will be regarded as unevaluable for the primary endpoint.

	Day 1 (baseline)	Day 28 ± 5 days (end of study)
Clinical examination	x	x
OHIP-14	x	x
Patient Reported Outcomes	x	x

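### The primary comparison drops and replaces patients because of what happens after randomisation (new immunomodulatory drug, low rinse use), and no all-randomised analysis is planned

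*Combined protocol and SAP*

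**What the plan says.** Section 12 (Protocol Violations) defines two groups by events during treatment.

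- **Added medication.** New immunomodulatory drugs, systemic or topical in the mouth, are permitted during the four weeks, but "these patients will be regarded as unevaluable for the primary endpoint and will be replaced". Section 9.2 has a parallel rule for worsening disease that needs such a drug: "patients will remain on treatment, but will be regarded as unevaluable for the primary endpoint".
- **Low rinse use.** The second group is those "who use the treatment fewer than 2 times a day for more than 2 weeks". Rinse use is judged late, "as determined by review of the treatment diary at the week 4 visit". The consequence for this group is that they "will be considered unevaluable for the primary endpoint and replaced with new patients". Their data still count for toxicity reporting.

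Section 12.4 adds: "Subjects who withdraw from the study treatment will be replaced". It does not say whether their scores are used. Section 8.1 describes a predetermined computer-generated list but not how replacements are allocated.

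Section 13.1.1 compares change in VAS between arms by t-test or Mann-Whitney test and names no analysis population. Section 13 promises a detailed SAP before the final analysis.

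Three statements on added medication do not agree. Section 7 says "There will be no restrictions on concomitant medications or supportive care measures". Section 9.2, speaking of the disease under study, says "No investigational or commercial agents or therapies other than those described below may be administered with the intent to treat". Section 12 permits new immunomodulatory drugs.

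**The concern.** Randomisation makes the arms comparable at baseline. That protection covers everyone randomised, not a subset chosen by later events.

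Both filters can depend on the assigned rinse. The vehicle differs between arms, and the study rationale argues that Mucolox may improve compliance. The decision to add a drug is made with the arm known (section 8.2), and section 9.2 links it to worsening of the disease being measured. The endpoint is the patient's own rating of worst sensitivity (section 9.2.3). Low use is judged at the visit where the outcome is collected.

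Replacement restores the count but not the comparison, because the patient who left was removed for something that happened after assignment. What is at stake is whether the trial's main efficacy contrast estimates the effect of assigning the Mucolox formulation.

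**Working it through.** **1. The plan's own figure.** Section 13.2 gives mean reductions of 6.5 (Arm A) and 4.5 (Arm B), SD 1.4, two-sided alpha 0.05, at least 80% power, 15 per arm and 5% loss to follow-up. A two-sample t-test for a difference of 2.0 needs 9 per arm, and 9/0.95 rounds up to 10. So 15 per arm satisfies the power statement but exceeds what these inputs require. Power at 15 per arm is 96.5% (noncentral t). No rate of unevaluable patients is given.

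**2. Spurious difference when the arms are truly equal.** Assume change is normal with mean 4.5 and SD 1.4 in both arms. The removal shares s are assumptions.

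- *Removed at random from the lower half of responders.* The lower-half mean is 4.5 − 1.4 × 0.798 = 3.383. The mean left is (4.5 − s × 3.383)/(1 − s): 4.559 at 5%, 4.624 at 10%, 4.779 at 20%.
- *Strictly the lowest responders removed.* The mean left is 4.5 + 1.4 × φ(z)/(1 − s), where z is the s-quantile and φ the standard normal density: 4.652 at 5%, 4.773 at 10%, 4.990 at 20%.

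| Removed A / B | Lower half | Strictly lowest |
|---|---|---|
| 10% / 5% | 0.07 | 0.12 |
| 20% / 5% | 0.22 | 0.34 |
| equal shares | 0 | 0 |

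The arm that loses more patients looks better. In simulations with 15 evaluable per arm and the strictly lowest removed, two-sided type I error is about 0.05 at 10%/10%, about 0.06 at 10%/5%, between 0.11 and 0.12 at 20%/5%, and about 0.17 at 20%/0%.

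**3. Gap between the two comparisons when evaluable patients are as planned.** Let m be the mean change of removed patients, assumed 0 to 4.5, or 6.5 if added therapy works well. If evaluable patients change by 6.5 and 4.5, the plan reports 2.0. The all-randomised difference is:

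- 10%/5%: (0.90 × 6.5 + 0.10m) − (0.95 × 4.5 + 0.05m) = 1.58 (m = 0), 1.80 (m = 4.5), 1.90 (m = 6.5).
- 20%/5%: (0.80 × 6.5 + 0.20m) − (0.95 × 4.5 + 0.05m) = 0.93, 1.60, 1.90.
- 10%/10%: 0.90 × 2.0 = 1.80 for any m.

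The gap can also run the other way. If evaluable change is 4.5 in both arms and removal is 5%/25%, the plan reports 0, while the all-randomised difference is 0.90 (m = 0), 0 (m = 4.5) or −0.40 (m = 6.5).

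**4. Power for all randomised patients at 15 per arm.** If the changes in section 13.2 describe everyone randomised, it is the 96.5% above. If they describe evaluable patients only, the mixture lowers the difference and widens the spread. With 10% affected per arm and m = 0 the difference is 1.8 and the SD about 2.18. Simulated t-test power (40,000 trials, SD 1.4 within each subgroup) is then 59% (m = 0) to 90% (m = 4.5). With 20%/5% affected it is 21% to 79%.

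**The case against.** **No removal rates, and the same drug in both arms.** Drug, concentration and schedule match, and nothing in the documents predicts unequal removal. The spurious differences are small beside the planned 2.0 points, and type I error is clearly inflated only when removal is quite unequal and falls on the worst responders. This stands, and it limits any claim about size. It does not remove the structural fault: the vehicle differs, the trial is open label, and at 15 per arm one or two patients are 7% to 13% of an arm.

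**Step 3 compares two target quantities.** It does not show bias under no effect. That is right; only step 2 does so.

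**The SAP is still to come and can define the population.** True, but the rule is protocol text applied during conduct. The promise of a SAP does not say these patients will be restored, and a week-4 score not sought at the time cannot be recovered later.

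**Stronger readings that a reader might infer.**

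- *That the filters keep only full compliers or good responders.* They do not. The rinse rule is a threshold: none for 14 days and two a day for 14 days is 28 of 84 scheduled rinses and does not trigger it. A poor responder who adds nothing also stays evaluable.
- *That the 28-rinse patient certainly stays in.* This is not settled either. Non-compliance is a listed violation in section 12 and a possible reason for discontinuation in section 11.1, and section 12.4 replaces patients who withdraw from treatment.
- *That the plan already secures every week-4 score.* Sections 11.1 and 12.3 ask for an early visit and encourage later attendance, but an early visit may not yield a week-4 score.

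**Conclusion.** The point holds. As written, the primary comparison is between patients who pass post-randomisation filters, one of them tied to worsening disease, and nothing in the current text provides an all-randomised comparison. It should be fixed before the plan is applied, because it concerns the trial's main efficacy contrast.

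Size and direction are unknown. The illustrations of 0.07 to 0.34 points in favour of the arm with more removals rest on assumed rates and on poorer responders being the ones removed. Equal removal from equal arms gives no bias. A reader might infer that the rule favours Mucolox; the documents do not support that, since either arm could lose more. A reader might also infer that an all-randomised analysis must be badly underpowered. That follows only if the changes in section 13.2 describe evaluable patients, which the plan does not say. The conclusion rests on the stated rule and not on any one of these figures.

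**What to change.** Change the analysis only; no clinical rule is proposed.

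1. Remove the wording in sections 9.2 and 12 that makes these patients unevaluable for the primary endpoint.
2. Make the primary analysis all randomised patients in their assigned arm, on observed week-4 worst-sensitivity scores whatever the compliance or added medication. Randomise any replacements from the list and add them without displacing anyone.
3. Keep the plan's evaluable set as a supportive per-protocol analysis.
4. Add a sensitivity analysis that ranks patients with new immunomodulatory therapy as no improvement, because observed scores credit the added drug to the assigned rinse.
5. Seek the week-4 score from patients who stop early, and state how an early-discontinuation score is used.
6. For scores never obtained (the plan expects 5%, which is 0.05 × 30 = 1.5 patients), state a simple method in advance, for example imputation from baseline and arm, with a no-change sensitivity analysis. Use diary data only where a diary is returned: patients bring diaries to the visit (section 8.6), so those who never return will usually leave none.
7. Reconcile sections 7, 9.2 and 12 on added medication, so that the event in item 4 has one definition.
8. State whether the changes in section 13.2 describe all randomised or only evaluable patients, and give power for the all-randomised analysis.

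The cost is protocol and SAP wording, some follow-up effort and possible dilution. On the evaluable-only reading with 10% affected per arm, adding replacements (about 33 randomised in all) brings t-test power to about 64% to 93%, against 59% to 90% at exactly 15 per arm. It is lower if Arm A loses more than Arm B: at 20%/5%, 23% to 86% with replacements (about 35 randomised).
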